Phentermine as a monotherapy is FDA-approved for short-term treatment of obesity in adolescents ≥17 years. Topiramate has long been used in pediatrics for epilepsy and migraine prevention, and has been studied as an anti-obesity medication in adolescents. ²² Among the 5 medications FDA-approved for long-term treatment of obesity in adults, the combination of phentermine and extended release (ER) topiramate results in the most weight loss at 1 year in placebo-controlled clinical trials (~20lbs, 15mg/96mg dose; ~15lbs, 7.5mg/46mg dose). 23 In two large RCTs of phentermine/topiramate in adults, the odds ratio (OR) for achieving ≥10% weight loss was 11.34, and the OR for discontinuation of drug due to adverse events was 2.32 vs. placebo.²⁴ This drug combination has never been prospectively studied for obesity treatment in adolescents, despite its frequent empiric clinical use with good patient tolerance. Phentermine acts as a central nervous system stimulant through norepinephrine reuptake inhibition, resulting in appetite suppression and increased resting energy expenditure.²⁵ Topiramate's exact mechanistic effect on appetite is unclear, but is likely linked to central GABA and dopamine modulation. 25 The only RCT of topiramate for weight loss among adolescents was a pilot study in a non-surgical setting that evaluated 24 weeks at 75mg/day and found no significant difference in mean percent change in BMI, but this may have been affected by the study's 4-week run in of meal replacement.²² A retrospective review of 15mg/day phentermine + SOC vs. SOC alone among adolescents with obesity/severe obesity demonstrated a greater percent decrease in BMI at 6 months in the phentermine + SOC group vs. matched controls, with no between-group differences in blood pressure. 26 After bariatric surgery, several retrospective studies in adults have shown significant beneficial effects of anti-obesity medications (including phentermine, topiramate, and the combination) in halting weight regain and achieving additional weight loss after plateau. 27-30

Additionally, the first ever framework for the use of anti-obesity medications in adolescents

highlights the post-surgical period as one setting for which pharmacotherapy should be considered, but without a supporting evidence base.³¹ Thus, studies of anti-obesity pharmacotherapy in adolescents are needed.

III. Preliminary Studies

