the participant in advance of the informed assent discussion using REDCap's survey distribution tool. The eAssent form is designed to allow the participant to navigate forward and backward through the entire form and to access the form at a later time if desired. During the informed assent discussion, the potential participant's questions will be answered and at the end, the participant will verbally confirm they agree to be in the study. Because there can only be one signature ("certifier") for each REDCap eAssent form, there are separate REDCap eAonsent forms for the adolescent/young adult and the researcher presenting the form. The eAssent gives subjects the option to download a copy of the signed form. If a participant refuses or is unable to eAssent but is still interested in participating, a physical assent will be collected by the study team at the next inperson visit to the bariatric surgery center.

C. Study Design and Research Methods

Figure 1. Study Design

The pharmacotherapy group will receive oral phentermine and immediate release topiramate in combination, up-titrated to goal doses of 16mg and 100mg, respectively over 4 weeks*, then maintained at this dose for 8 additional weeks. Topiramate is gradually down-titrated during weeks 13 and 14 to prevent possible discontinuation symptoms.

Dosing Schedule^{†,§}

Uptitration:

- Week 1: 4mg phentermine + 25mg immediate release topiramate
- Week 2: 8mg phentermine + 50mg immediate release topiramate
- Week 3: 12mg phentermine + 75mg immediate release topiramate

Goal Dose:

- Weeks 4-12: 16mg phentermine + 100mg immediate release topiramate **Discontinuation (at study Visit 4)**:
- Week 13: Discontinue Phentermine + Decrease topiramate to 50mg
- Week 14: Decrease topiramate to 25mg for 7 days, then discontinue
- (*) Participants who do not tolerate goal doses will be maintained at the highest tolerated dose. (§) Per existing literature³⁴ and discussion with pharmacy, participants with moderate hepatic impairment (ALT >3x ULN but <10x ULN on two consecutive measures outside of acute illness, and no evidence of hepatic synthetic dysfunction), will follow the same dosing schedule, with doses reduced as needed

based on side effects (See Procedure for Study Drug Dose Reduction/Discontinuation).

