Nausea, Vomiting, Diarrhea	DSMP				
Rare, but Serious ⁴⁰					

Acute myopia, Secondary angle closure glaucoma	DSMP
Oligohidrosis, Hyperthermia	DSMP (including temperature at every study visit)
Metabolic acidosis	Bicarbonate at enrollment, visit 2, and visit 4
Suicidal ideation/attempt	DSMP with assessment at every study visit
Fetal toxicity	Pregnancy tests at enrollment and every study visit
(Pregnancy Risk Factor Category D- positive evidence of risk)	Requirement for females to either have a LARC (majority) or documented commitment to use 2 forms of birth control
Withdrawal symptoms	Gradual discontinuation at the end of the study
Hyperammonemia and encephalopathy	Drug interaction check; DSMP
Kidney stones	BMP at enrollment, visit 2, and visit 4; Drug interaction check; DSMP
Topiramate-Ethanol interaction (potential to cause increased CNS depression)	Counseling about alcohol avoidance, and specific language about this risk in the consent/assent

Methods for systematically assessing changes in mood, suicidality, and cognition.

Mood:

Changes in mood will be systematically screened for using the Center for Epidemiologic Studies Depression Scale (CES-D). This is a 20-item self-report questionnaire that covers areas including depressed mood, feelings of guilt/worthlessness, helplessness, psychomotor retardation, loss of appetite and sleep disturbance over the previous week. ⁴⁶ This instrument has yielded adequate internal reliability that is robust to age, clinical vs. nonclinical setting, and risk of bias. ⁴⁷ The original version of the measure is appropriate for individuals 12 years of age and older. The CES-D is routinely administered to individuals receiving care at the Children's Colorado Bariatric Surgery Center at every follow-up pre-operative and post-operative clinic appointment.

The proposed study will additionally administer the CES-D at all study visits not aligned with a clinical visit and will be scored by the PI or professional research assistant. A CES-D score <20 indicates no to mild depressive symptoms. And a CES-D score ≥20 indicates elevated depressive symptoms. This is based on a metaregression that supported higher cut points having better diagnostic accuracy.⁴⁷

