- -Comprehensive review of systems at every study visit (to capture possible AEs not reported previously)
- -Physical exam at every study visit (e.g. new murmurs, rubs, or gallops, new increased work of breathing, new pulmonary edema, new peripheral edema);
- -Vitals at every study visit (e.g. new fever, tachycardia, new elevated blood pressure/hypertension)
- -Phone call 1, 2, and 3 weeks after study drug initiation and in-person with a questionnaire at visits 2, 3, and 4 to review known possible side effects of phentermine and topiramate
- -Lab monitoring: basic metabolic panel (to assess for new metabolic acidosis: bicarb < 18 mmol/L); urine pregnancy tests for all females at every visit.
- -Monitoring of mood, suicidality, and cognition per above with validated assessments at enrollment and every study visit (e.g. new or worsened depression, new suicidal ideation/behavior)
- -Between study visits, participants with questions about symptoms will also be encouraged to call the PI directly (voicemail messages are forwarded to the PI's password-protected email)
- 3. To what external entities will local adverse events be reported?: In addition to COMIRB, the PI will report local adverse events to the FDA, according to their safety reporting requirements: https://www.fda.gov/downloads/Drugs/Guidances/UCM227351.pdf). Specifically, the PI will report to the Division of Metabolism and Endocrinology within the FDA's Center for Drug Evaluation and Research, which reviewed the IND application for this study. The PI will report to this Division: 1) Any unexpected fatal or life-threatening suspected adverse reactions no later than 7 calendar days after initial receipt of the information, and 2) Any a) serious, unexpected suspected adverse reactions, b) findings from other clinical/animal/in-vitro studies

that suggest significant human risk, and c) a clinically important increase in the rate of serious suspected adverse reactions no later than 15 calendar days after determining that this information qualifies for reporting.

4. Will periodic global review of safety/adverse events (serious adverse events and adverse events) occur?: Yes, reviews will be performed by the PI, and a three-member data and safety monitoring board (DSMB), including a primary Safety Officer.

Reviewer	Expertise	Review Frequency	Written Reports	Report Frequency

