Route of Data Collection: To reduce in-person time on campus for participants, components of Study Visits 1-4 will be collected remotely (designated by superscript "R" in Table 3 below) either via secure video call or telephone call (with questionnaires emailed) in the participant's/guardian's preferred language within the same week and ideally on the same day as the study visit. These measures will be conducted remotely unless it is not possible or places an undue burden on the participant to do so (e.g. participant does not have a reliable internet connection or has a limited phone data plan that incurs significant charges). Pill count will require a video connection. All other measures require in-person collection/administration to appropriately collect outcome/safety data.

Table 3. Schedule of Measures

"X"= Study specific "O"= Standard of Care #= Bariatric Clinic or CHCO CTRC ‡= + Adult CTRC or CHCO Radiology/CTRC R= can be delivered remotely	SCREENING/ ENROLLMENT# 6-12 mo post- op	STUDY VISIT 1#,‡ ~1wk after Enrollment	STUDY VISIT 2# 4wks after Visit 1	STUDY VISIT 3# 4 wks after Visit 2	STUDY VISIT 4#,‡ 4 wks after Visit 3
Review of Inclusion/Exclusion criteria	Х				
Echocardiogram (ONLY for those with Hypertension or Severe OSA with poor PAP adherence IF not obtained in the prior 6 months)	0				
Demographics Form		X ^R			
Feasibility of protocol implementation (e.g. enrollment rates, dropout rates)	х	х	X	х	X
Study medication adherence & tolerability- Study Med Form			X ^R	X ^R	X ^R
Study medication adherence- (pill count)- Study Med Form			X ^R	X ^R	X ^R
Study medication adherence (urine amphetamine screen)		X	X	X	X
Review of all non-study medications (self-report)	Х	X ^R	X ^R	XR	X ^R
Patient/family satisfaction survey					X ^R
Weight, Height, Temperature, HR, BP; Review of Systems; Physical exam		X	Х	X	X
Urine pregnancy test	X	X	X	X	X
Lipid panel, ALT, HbA1c	Х				Х
Basic metabolic panel	Х		Х		X
Optional Biobanking	Х		Х		X
3-day diet record review		X ^R			X ^R
Previous Day Physical Activity Recall (PDPAR)		X ^R			X ^R

IWQOL-Kids (≤19yo)/-Lite (≥ 20yo) & Parent Report		X ^R			X ^R
PedsQL (general health-related quality of life)		X ^R			X ^R
CES-D (Depression Screen)	0	X	X	Χ	X
C-SSRS (Suicide Screen)	X	X	X	Х	X
Resting metabolic rate		X			X
DEXA-3 site		X			Х
Clinical Intervention/Translation Core: Eating behavior questionnaires (VAS, TFEQ, EAH)		X ^R	X ^R	X ^R	X ^R

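### Participants who enter with ALT above 3x but below 10x ULN have no scheduled ALT until dosing ends; adding ALT to the existing Visit 2 draw would be a cheap improvement, not the correction of an error

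*Combined protocol and SAP*

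**What the plan says.** **Who may enter.** The exclusion criteria (section IV.B) rule out ALT above 10x ULN or known synthetic liver dysfunction. The hepatic footnote to the Dosing Schedule (section IV.C) defines a moderate group, "ALT >3x ULN but <10x ULN on two consecutive measures outside of acute illness", without synthetic dysfunction. It says that they "will follow the same dosing schedule, with doses reduced as needed" on the basis of side effects. The footnote cites literature and pharmacy advice for this rule and adds a pointer: "See Procedure for Study Drug Dose Reduction/Discontinuation". No section with that title appears in the supplied text.

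**When ALT is measured.** The Table 3 row "Lipid panel, ALT, HbA1c" is marked at Enrollment and Visit 4 only. The basic metabolic panel is marked at Enrollment, Visit 2 and Visit 4.

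**What is monitored, and why.** Item 2 of the Data and Safety Monitoring Plan (DSMP) gives "Lab monitoring: basic metabolic panel (to assess for new metabolic acidosis: bicarb < 18 mmol/L" plus urine pregnancy tests. Table 2 ties the repeated tests to named topiramate risks: "Bicarbonate at enrollment, visit 2, and visit 4" for metabolic acidosis, and "BMP at enrollment, visit 2, and visit 4" for kidney stones. It lists no ALT rise or liver injury for either drug. The drug discontinuation criteria (DSMP item 6) contain no ALT criterion.

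**How the plan regards ALT.** It is an Aim 3 outcome. Baseline ALT review is also a risk-mitigation step for each drug, and item f of the data collection tools groups ALT with outcome and safety measures.

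**The concern.** The plan treats ALT as relevant to safety at entry: it sets an upper limit and calls for baseline review. It then knowingly admits people below that limit but well above normal, and schedules no further ALT until the visit at which phentermine stops and the topiramate taper begins. A participant who enters at, say, 9x ULN could pass the level that would have kept them out, and no scheduled test would show it while the result could still change goal-dose treatment.

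The other safety checks are calls in weeks 1 to 3, symptom questionnaires, review of systems, and a physical examination at each visit. They can pick up symptoms but not a silent rise. DSMP item 2 counts an abnormal laboratory value as a possible adverse event, but such a value has to be measured to be recorded. The Background says of the combination: "This drug combination has never been prospectively studied for obesity treatment in adolescents". The same sentence adds that it is often used empirically and well tolerated.

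At stake is the timing of safety information for a small subgroup of a 14-person pilot. No estimate, endpoint or test depends on it.

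**Working it through.** The plan gives no figure for the ALT interval, so there is none to reproduce. The interval follows from the visit spacing in Table 3. Drug start is taken as Visit 1, which fits the calls placed 1, 2 and 3 weeks after it.

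**Inputs**
- Enrollment to Visit 1: about 1 week. Visits 1 to 2, 2 to 3 and 3 to 4: 4 weeks each (Table 3).
- Goal dose: weeks 4 to 12, which is 12 − 4 + 1 = 9 weeks (Dosing Schedule; section IV.E also gives 9).
- Randomized: 14 (section IV.B).

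**Current schedule**
- Weeks from Enrollment: Visit 1 = 1; Visit 2 = 1 + 4 = 5; Visit 3 = 5 + 4 = 9; Visit 4 = 9 + 4 = 13.
- Gap between scheduled ALT values: 13 − 0 = about 13 weeks.
- First on-drug ALT: 13 − 1 = 12 weeks after drug start, so the gap spans all 12 dosing weeks.

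**With ALT at Visit 2**
- Gaps: 5 − 0 = about 5 weeks, then 13 − 5 = 8 weeks. The longest falls from 13 to 8.
- First on-drug ALT: 5 − 1 = 4 weeks after drug start.
- Visit 2 falls at the end of week 4, so 1 goal-dose week is complete and 9 − 1 = 8 remain (8/9 = 89%).

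**Do routine clinic laboratory tests fill the gap?** Section IV.D places them at 6, 9 and 12 months after surgery. For participants enrolled at 6 or 9 months, Visit 4 typically coincides with the next of these. For those enrolled at 12 months, no later routine draw is listed. If enrollment is out of step with the clinic calendar, a routine draw could fall inside the gap, but the plan does not say that the routine panel includes ALT.

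**Why a fixed limit is not enough.** The rise needed to reach 10x ULN depends on the starting value:
- from 1x: 10/1 = 10-fold
- from 3x: 10/3 = 3.3-fold
- from 9x: 10/9 = 1.11-fold

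A criterion relative to the participant's own baseline helps at the low end of the group, and the 10x limit helps at the high end. With a relative criterion of k times baseline, the 10x limit is reached first for anyone entering above 10/k. For k = 2 that is 5x ULN; for k = 1.5, 6.7x; for k = 3, 3.3x. These values of k are assumptions; the documents give none.

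**Number of assays.** Between 0 and 14 if limited to entrants above 3x ULN, because their number is not given; at most 14 if done for everyone.

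**The case against.** The strongest case against is that the monitoring matches the listed risks. Bicarbonate and the metabolic panel are repeated at Visit 2 because Table 2 links them to acidosis and kidney stones. Neither drug has a listed liver reaction. The nearest entry, hyperammonemia with encephalopathy, has its own mitigation and discontinuation criterion, and ALT does not measure ammonia. The hepatic footnote reads as a rule about tolerating the dose with existing liver impairment, which is why side effects are its trigger. The plan also cites long pediatric experience with topiramate, often at 200 to 400 mg/day against 100 mg here, and reports no evidence of added risk from the combination. This stands, and it keeps the expected yield low.

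A reader might infer that repeating the metabolic panel at Visit 2 without ALT is an inconsistency. It is not: the two tests serve different stated purposes, and the plan nowhere promises ALT as an on-treatment safety test.

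A reader might also infer that the trial has no provision for this group during treatment. The documents do not support that either. Doses can be reduced for side effects, and the procedure named in the footnote may call for repeat laboratory tests outside Table 3. The finding is therefore limited to the supplied text.

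The footnote's requirement of two consecutive values adds little. Table 3 has one ALT before dosing, but an earlier clinic value may supply the other, and the group follows the same schedule in any case.

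What survives is narrower. The plan sets a limit of 10x ULN at entry, admits people below it, and in the supplied text schedules no test that could show during treatment that the limit has been passed.

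**Conclusion.** The point holds as a low-cost improvement of low expected yield. It is not an error. The scheduled ALT interval of about 13 weeks covers the whole dosing period. One added value at Visit 2 would give a result about 4 weeks after drug start, with 8 of 9 goal-dose weeks left, and would cut the longest gap to 8 weeks. Any action that waits for a confirmatory test would come somewhat later than Visit 2.

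This rests on three things: Table 3 being the complete ALT schedule, dosing starting at Visit 1, and at least one participant entering above 3x ULN. The first is uncertain because the cited procedure is not in the supplied text. The third is unknown, and the number may be zero. The documents do not support a claim that the drugs are expected to harm the liver or that participants are exposed to a quantified hepatic risk. No endpoint or planned analysis is affected.

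**What to change.** - For participants entering above 3x ULN, and optionally for all, add ALT to the blood already drawn at Visit 2. Section IV.D already assigns a research nurse to that draw.
- Enter it in Table 3 and in the laboratory item of DSMP item 2.
- Have the principal investigator compare the result on receipt with the participant's Enrollment value. A value above 10x ULN, or a rise meeting a criterion that the Safety Officer approves in advance (a role already given in DSMP item 4), would prompt a repeat ALT and a dose review. It would not stop the drug automatically. One possible criterion is a value above ULN and at least 2x baseline; the factor of 2 is an assumption, with 1.5 to 3 a reasonable range to discuss.
- If the procedure cited in the hepatic footnote already requires such tests, a cross-reference in Table 3 is enough.

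**Cost.** At most 14 assays with no extra scheduled venipuncture, some amendment wording, and one criterion to approve. The documents give no assay price, so the low cost is inferred from the existing draw. Downsides are incidental findings and, for anyone meeting the criterion, a confirmatory draw. That draw might need an added visit, because Table 3 has no blood draw at Visit 3. Between Visit 2 and Visit 4 there would still be 8 weeks without a scheduled ALT.

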Prior to study start, within the Bariatric Surgery Center, we had managed 13 patients perioperatively on phentermine, topiramate, or the combination for weight stabilization/loss. The PI and primary mentor continue to manage many additional patients on topiramate and phentermine in the broader Lifestyle Medicine weight management program at Children's Colorado, and we have developed clinical guidelines for the use of these medications at CHCO. In our perioperative experience, these medications are generally very well-tolerated.

Given the current Food and Drug Administration labeling for each of the proposed study drugs, the PI has successfully obtained an Investigational New Drug Application (IND 142590) for this pilot study. The IND is active for the use of phentermine and immediate release topiramate in 12-24 year olds after bariatric surgery as defined in this research protocol. We will follow a data and safety monitoring plan (see page 12), which includes an appointed Safety Officer in conjunction with IRB approval and study launch.

IV. Research Methods

A. Outcome Measure(s):

Primary Aim 1:

Feasibility

• Protocol Implementation: recruitment, enrollment, randomization, and dropout rates

 Acceptability: Adherence to medication: Self-report by questionnaire, pill counts and urine amphetamine testing | *Tolerability to medication*: Self-report by questionnaire assessing effects, side effects, barriers to adherence, and standardized assessment of possible adverse effects by study staff

Secondary Aim 2:

· Weight, BMI

Secondary Aim 3:

- Manual blood pressure
- Fasting lipid panel: Total cholesterol, HDL, non-HDL, LDL, Triglycerides
- Alanine aminotransferase (ALT) as a surrogate for non-alcoholic fatty liver disease improvement
- Hemoglobin A1c (HbA1c)
- Dietary intake
- Resting metabolic rate
- Body composition and Bone density
- Eating behaviors
- Physical activity
- Quality of Life

B. Description of Population to be Enrolled:

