At 1, 2, and 3 weeks after study medication initiation, weekly during any additional titration during the protocol, and at each study visit, participants will be asked to complete a self-report checklist of possible adverse effects that have reported associations with the active study drugs, which include changes in memory, attention/concentration, word-finding/language, and overall academic/job performance, along with the perceived severity of each (mild, moderate, or severe).

Severe cognitive difficulty, which is a drug dose reduction/discontinuation criteria, will be defined as self-report of a "severe" change in memory, attention/concentration, or word finding/language that the participant believes is significantly impacting academic or job performance and that is not otherwise explained by non-study medication related factors.

Of note, in the one randomized controlled trial of topiramate for weight loss among severely obese adolescents⁵⁰ (24-week intervention of 75mg/day topiramate vs. placebo), Fox et al. found no significant differences between topiramate and placebo groups on subscales of the Cambridge Neuropsychological Test Automated Battery (CANTAB) or Behavioral Rating Inventory of Executive Function-Self Report (BRIEF-SR), and on the Connors Continuous Performance Test II (CPT II), the only significant finding was faster reaction time in the topiramate group compared to the placebo group.

2) Data and Safety Monitoring Plan (DSMP):

Definitions: The PI will use the FDA's/Center for Drug Evaluation and Research's "Guidance for Industry Investigators Safety Reporting Requirements for INDs and BA/BE Studies" document to define the terms: adverse event (AE), suspected adverse reaction, adverse reaction, unexpected, serious, and life-threatening.

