In addition to the above in-person study visits and designated remote data collection, there are eight standard study phone calls in the protocol:

- Phone Call 1: 1-2 days before the Screening/Enrollment Visit 0 (Reminder to fast)
- Phone Call 2: 1 week before Visit 1 (Phone Call Script 1)
- Phone Call 3: 1 week after Visit 1 (Phone Call Script 2)
- Phone Call 4: 2 weeks after Visit 1 (Phone Call Script 2)
- Phone Call 5: 3 weeks after Visit 1 and 1 week before Visit 2 (Phone Call Scripts 1 & 2)
- Phone Call 6: 1 week before Visit 3 (Phone Call Script 1)
- Phone Call 7: 1 week before Visit 4 (Phone Call Script 1)
- Phone Call 8: 1 week after last dose of study drug (Phone Call Script 2)

If a participant requires additional dose titration during the protocol, the PI will conduct additional weekly phone calls until study medication dosage is stable.

E. Potential Scientific Problems:

Benchmarks for success, pitfalls, and alternatives:

Primarily, we expect this protocol to demonstrate feasibility, which will form the foundation for a larger study of pharmacotherapy as an adjunct to bariatric surgery. Secondarily, we expect to demonstrate short-term efficacy of pharmacotherapy in terms of promoting additional weight loss and improving biological markers.

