Sample size justification: Based on recommended practice for pilot studies, 60 the minimum sample size (10 total participants, 5 per arm) is driven by the primary aim of the study and represents a balance between participant availability (patient volume and recruitment timeline), and acceptable precision around feasibility estimates (Aim 1), which will be used for subsequent study planning. It is not based on a power calculation for group differences seen in any Aim 2 or 3 measures. To estimate precision around dropout and medication tolerability rates, we used a confidence interval approach with normal approximation of the binomial calculation 60-62. First, we estimate that a realistic dropout rate is 25%, based on 3 prior anti-obesity medication RCTs conducted in obese adolescents. 22,63,64 A realistic medication tolerability rate (% who do not discontinue medication because of adverse effects) is 85%, based on the single RCT of topiramate in adolescents and two larger RCTs of phentermine/topiramate XR in adults. ^{22,65,66} Dropout: With the minimum of 10 adolescent/young adult participants, if our observed dropout rate is 25%, we can be 68% confident that the enrollment rate estimate is accurate within 13 percentage points (or 90% confident that it is accurate within 20%). With 14 adolescent/young adult participants, if our observed dropout rate is 25%, we can be 68% confident that the enrollment rate estimate is accurate within 11 percentage points (or 90% confident that it is accurate within 18%). Medication tolerability: With 10 adolescent/voung adult participants, if our observed medication tolerability rate is 85%, we can be 68% confident that the tolerability estimate is accurate within 9 percentage points (or 90% confident that it is accurate within 16%). With 14 adolescent/young adult participants, if our observed medication tolerability rate is 85%, we can be 68% confident that the tolerability estimate is accurate within 9 percentage points (or 90% confident that it is accurate within 15%). Given possible constraints around enrollment, the level of precision with 10 or 14 adolescents/young adults was deemed acceptable to achieve protocol refinement for future RCT development.

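### The safety plan claims validated cognition assessment at enrollment that the protocol does not provide, and its sections conflict on whether the adverse-effect checklist is given before the first dose

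*Combined protocol and SAP*

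**What the plan says.** Section IV.A (Outcome Measures) lists tolerability under Primary Aim 1, measured by "Self-report by questionnaire assessing effects, side effects, barriers to adherence, and standardized assessment of possible adverse effects by study staff". Under Planned analyses (section F), acceptability, including tolerability, is described by between-arm differences in proportions.

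Section IV.D.2 (Data and Safety Monitoring Plan), item 2, describes "Monitoring of mood, suicidality, and cognition per above with validated assessments at enrollment and every study visit". The same list places the side-effect review at calls 1, 2 and 3 weeks after drug start and "in-person with a questionnaire at visits 2, 3, and 4 to review known possible side effects of phentermine and topiramate".

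The Cognition section, to which item 2 refers back, says that at weeks 1, 2 and 3, during any extra titration, and "at each study visit, participants will be asked to complete a self-report checklist of possible adverse effects". The cognition items on that form ask about changes in memory, attention, language and school or job performance, each rated mild, moderate or severe.

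Table 3 has a row "Study medication adherence & tolerability- Study Med Form", marked at Visits 2, 3 and 4 and blank at Enrollment and Visit 1.

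The sample size justification (section F) works with a different quantity: "A realistic medication tolerability rate (% who do not discontinue medication because of adverse effects) is 85" per cent.

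**The concern.** The safety plan describes a baseline cognition measurement that no other part of the protocol supplies. Anyone relying on that sentence would believe that cognitive change, which the protocol itself treats as a topiramate risk, is tracked from enrollment with a validated tool.

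The second issue is the missing baseline for the checklist as a whole. Effects such as fatigue, dizziness or poor concentration may already be present in adolescents 6 to 12 months after bariatric surgery. If the form is first completed after dosing, a ticked symptom may be new, worse or unchanged, and the form cannot show which. The pilot's tolerability figures are meant to inform a larger trial, so absolute symptom rates that include background complaints would carry forward. The definition of severe cognitive difficulty also rests on a change, with no earlier reading on the same form to document it.

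**Working it through.** **The plan's own figure.** The only number tied to tolerability is the precision around 85% with 14 participants, stated as 9 points (68% confidence) and 15 points (90%). The formula is z × √(p(1−p)/n). With p = 0.85 and n = 14, the root is 0.0954, giving 0.994 × 0.0954 = 9.5 points and 1.645 × 0.0954 = 15.7 points. With p = 12/14 the results are 9.3 and 15.4, which round to the stated values. The figure concerns discontinuations, so the point made here does not change it.

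**The sections side by side.**

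| Place | Cognition tool | Pre-dose reading? |
|---|---|---|
| Monitoring plan, item 2, mood/suicidality/cognition line | validated assessment | yes, at enrollment |
| Monitoring plan, item 2, side-effect line | questionnaire | no: weeks 1–3, Visits 2–4 |
| Cognition section | self-report checklist, no validation cited | Visit 1 if read literally; enrollment not listed |
| Table 3 | no cognition row; Study Med Form | no: Visits 2–4 |
| Phone-call list | Script 2 | no: first used 1 week after Visit 1 |

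The scripts are not reproduced; that Script 2 is the side-effect script is inferred from its timing. By contrast, Table 3 marks the depression scale and the suicide scale at Enrollment and at Visits 1 to 4. The validated cognitive batteries named in the Cognition section belong to a cited earlier trial.

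**Size of the effect.** The documents give no background symptom rate, so these inputs are assumptions. Let b be the share with a given symptom before dosing in both arms and r the share of symptom-free active participants who develop it. Assume no new cases on placebo, no worsening of existing symptoms, and every endorsement counted. Then:

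- Raw count: active b + (1−b)r, placebo b, difference (1−b)r.
- New symptoms over all randomized: active (1−b)r, placebo 0, difference (1−b)r.
- Standard error of the difference with 7 per arm: √[(p₁(1−p₁) + p₀(1−p₀))/7].

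For r = 30%:

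| b | Raw, active vs placebo | Ratio | SE (points) | New only, active vs placebo | SE (points) | Difference, either way (points) |
|---|---|---|---|---|---|---|
| 10% | 37% vs 10% | 3.7 | 21 | 27% vs 0% | 17 | 27 |
| 20% | 44% vs 20% | 2.2 | 24 | 24% vs 0% | 16 | 24 |
| 30% | 51% vs 30% | 1.7 | 26 | 21% vs 0% | 15 | 21 |
| 40% | 58% vs 40% | 1.45 | 26 | 18% vs 0% | 15 | 18 |

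At b = 30%: 0.30 + 0.70 × 0.30 = 0.51. The raw standard error is √[(0.51×0.49 + 0.30×0.70)/7] = 0.256; the new-symptom one is √[(0.21×0.79)/7] = 0.154.

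Zero new complaints on placebo is favourable. With 10% onset on placebo and b = 30%, the raw rates are 51% vs 37% and the new-symptom rates 21% vs 7%. The difference is 14 points both ways, with standard errors of 26 and 18.

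Randomization balances background symptoms only in expectation. The chance that at least one of 7 in an arm has the symptom before dosing is 1 − (1−b)⁷: 52% at b = 10% and 97% at b = 40%.

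**The case against.** A reader might infer that pre-existing symptoms are counted as effects of study drug in both arms. The documents do not support that. The monitoring plan defines an adverse event without any judgment about causality, and item 7 grades each event as definitely, possibly or not related. The cognition items ask about changes, and the severe-difficulty definition excludes problems explained by factors other than study medication. A review of systems takes place before dosing. The tolerability rate used for sizing counts discontinuations because of adverse effects, so a stable symptom ticked on a form does not enter it.

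A reader might also infer that the missing baseline shrinks the planned between-arm difference, for example from 30% vs 0% to 51% vs 30%. The 30% vs 0% comparison arises only by restricting the denominator to participants who were symptom-free before dosing. Over all randomized participants the difference is the same 21 points.

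Nor can it be said flatly that the checklist has no pre-dose administration, because the Cognition section can be read to include Visit 1.

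All of this stands. It does not supply the missing reading. The wording about change relies on recall and is stated only for the cognitive and performance items. Relatedness grading depends on temporal sequence, which a pre-dose reading would document. The review of systems is not described as recording the checklist's items or grades. Section IV.A also defines tolerability more widely than discontinuation, and the planned analysis does not limit it to related or new symptoms.

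**Conclusion.** The statement about validated cognition assessment at enrollment is wrong as written, and the Cognition section conflicts with the monitoring plan and Table 3 on whether the checklist precedes the first dose. These conclusions rest on the text alone.

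If the monitoring plan and Table 3 are followed, the questionnaire part of the tolerability outcome has no reading on the same form before dosing. Background symptoms would then raise the absolute rates in both arms, reduce the ratio and add noise. On the assumed inputs of 30% background and 30% onset on active, the active rate reads 51% instead of 21%, the placebo rate 30% instead of 0%, and the standard error about 26 points instead of 15. The expected difference in proportions is unchanged. These sizes depend on assumed rates and on every endorsement being counted, which no section specifies. For a descriptive pilot with 7 per arm the point is modest, but it concerns a primary-aim measure and is cheap to settle.

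**What to change.** 1. Reconcile the Cognition section, item 2 of the monitoring plan and Table 3 on when the checklist is given.
2. Add the checklist to Table 3 at Visit 1, before the first dose. Reword the items that ask about change to current presence and severity, since there is no drug exposure to change from at that visit, and use that wording throughout so that readings are comparable.
3. In Planned analyses, report symptoms that are new or have risen in severity grade since Visit 1, by arm and over all randomized participants, alongside the raw counts.
4. Correct item 2 so that validated assessment at enrollment refers to mood and suicidality only, and describe cognition monitoring as a self-report checklist.

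The cost is a few minutes at an existing visit, minor rewording of an existing form and text edits in these places. No new instrument is needed, and no dosing or discontinuation rule is touched.
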